7.1.1 Cohort trial treatment pausing rules

In this trial AEs and SAEs will be graded for the intensity using scales based on guidance from the US FDA “[Toxicity Grading Scale for Healthy Adult and Adolescent Volunteers Enrolled in Preventive Vaccine Clinical Trials](#)” (for further details, see Section 10.4.3):

If any of the below situations is observed in a given cohort, no further trial subjects will be assigned to the cohort and administration of trial treatment in the affected cohort and any higher DLs will be paused until IRC reviews the event(s):

- Any SAE developed by a subject administered the combination BNT162b4 + BNT162b2 Bivalent or BNT162b4 + BNT162b2 Monovalent (OMI XBB.1.5), or BNT162b4 alone (at any DL), for which there is no alternative, plausible, attributable cause and which is assessed by the investigator, or the sponsor as possibly related.
- Any Grade 4 AEs (solicited and/or unsolicited) after administration of combination BNT162b4 + BNT162b2 Bivalent or BNT162b4 + BNT162b2 Monovalent (OMI XBB.1.5), or BNT162b4 alone (at any DL) that is assessed as possibly related by the investigator, or for which there is no alternative, plausible, attributable cause.

- Any case of fever $>40.0^{\circ}\text{C}/>104.0^{\circ}\text{F}$ for at least one daily measurement persisting for over 6 h despite the use of antipyretic after administration of combination BNT162b4 + BNT162b2 Bivalent or BNT162b4 + BNT162b2 Monovalent (OMI XBB.1.5), or BNT162b4 alone (at any DL) that is assessed as possibly related by the investigator, or for which there is no alternative, plausible, attributable cause.
- If the IRC determines that $>20\%$ of trial subjects administered the combination BNT162b4 + BNT162b2 Bivalent or BNT162b4 + BNT162b2 Monovalent (OMI XBB.1.5), or BNT162b4 alone in the same cohort experienced the same or similar \geq Grade 3 or above unsolicited AE (including laboratory abnormalities) considered related, and/or for which there is no alternative, plausible, attributable cause.
- Any severe acute systemic hypersensitivity AE or anaphylactic reactions of Grade 3 that occurs within 7 d of trial treatment administration for which there is no alternative, plausible, attributable cause.
- Any case of myocarditis or pericarditis documented within 28 d after BNT162b4 + BNT162b2 Bivalent, BNT162b4 + BNT162b2 Monovalent (OMI XBB.1.5), or BNT162b4 alone administration with ECG or clinical laboratory findings supporting probable or possible myocarditis or pericarditis as per Brighton Collaboration Case Definition (see Section 8.3.8).

NOTE:

- Reactogenicity e-diary data confirmed by the investigator as being entered by the subject in error will not contribute toward a pausing rule.
- Data from recipients of BNT162b2 Bivalent alone will not support the pausing rules.

7.1.2 *Individual trial subject trial treatment pausing rules*

Trial treatment administration for an individual trial subject will be paused (if applicable), pending IRC review, if any of the below criteria are met:

- Safety concerns are identified by an investigator or the IRC.
- Permanent discontinuation (stopping) of trial treatment.

Trial treatment administration will be permanently discontinued for an individual trial subject if any of the below criteria are met.

- Any Grade 4 reactogenicity event considered to be related.
- Pregnancy.
- If a subject's trial treatment assignment is unblinded prior to Visit 5.

After pausing trial treatment according to Sections 7.1.1 or 7.1.2, the IRC may recommend a permanent discontinuation of trial treatment overall, in a cohort, or just for a single trial subject.

A permanent discontinuation of trial treatment may also occur for non-medical reasons at the judgment of the investigator or the subject (i.e., subject moves to a new location).

Trial subjects permanently discontinued from trial treatment will not be discontinued from the trial (i.e., will continue with trial visits and be evaluated for safety). The only exception is pregnant women who will not have further blood draws, but will otherwise complete all

planned assessments, if required including pregnancy follow-up as described in Section 10.5.3.

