In addition to the above safety reviews for dose modifications, other unplanned dose modifications, pausing (temporary halting) of trial treatment, or discontinuation of trial treatment may be required. See Section [7.1](#) for guidance on criteria for such cases.

For Dose 2 recipients, IRC safety review will be performed for the first 8 subjects 7 d post-Dose 2 in all DL cohorts (see [Table 1](#)).

Based on the WHO's recommendation, which has been endorsed by the FDA, and the FDA approval of BNT162b2 Monovalent (OMI XBB.1.5), Dose 2 for Cohorts 1 to 4 will be provided in line with current agency recommendations when available in the US. This will provide standard of care for vaccinees and carries a proven benefit for the current circulating XBB subvariants.

The dosing process for Cohort 5

For the dosing process schema for Cohort 5, see [Figure 2](#). Cohort 5 trial subjects will not be randomized and will be administered two doses of 30 µg BNT162b4 alone. An IRC safety review will be performed after all subjects receive Dose 2 (see [Table 1](#)).

Table 1: Schedule of IRC and safety reviews

Dose 1	Cohort 1	Cohort 2	Cohort 3a	Cohort 3b	Cohort 4a	Cohort 4b	Cohort 5
IRC contingent review (Gated) *	First 8 sentinel 7 d PD1 review approval needed prior to cohort expansion	First 8 sentinel 7 d PD1 review approval needed prior to cohort expansion	First 8 sentinel 7 d PD1 review approval needed prior to cohort expansion and enrollment of Cohort 3b		First 8 sentinel 7 d PD1 review approval needed prior to cohort expansion and enrollment of Cohort 4b		
IRC contingent review (Gated) *	Cohort 7 d PD1 review / approval needed prior to DL increase	Cohort 7 d PD1 review / approval needed prior to DL increase		Cohort 7 d PD1 review / approval needed prior to DL increase			
IRC safety review (Non-Gated) **				First 8 subjects 7 d PD1 reviewed		First 8 subjects 7 d PD1 reviewed	
Dose 2	Cohort 1	Cohort 2	Cohort 3a	Cohort 3b	Cohort 4a	Cohort 4b	Cohort 5
IRC safety review (Non-Gated) **	First 8 subjects 7 d PD2	First 8 subjects 7 d PD2	First 8 subjects 7 d PD2		First 8 subjects 7 d PD2		All Cohort 5 subject data up to 7 d PD2 reviewed

* Gated review: trial dosing is paused until IRC approves.

** Non-Gated review: trial dosing is not paused while awaiting IRC approval.

Abbreviations: d = day; DL = dose level; IRC = Internal Review Committee; PD1 = post-Dose 1; PD2 = post-Dose 2.

[figure not shown]

Figure 1: The staggered dosing process for Cohorts 1 to 4

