- Myocarditis and pericarditis are considered an important identified risk for BNT162b2 vaccines based on post-authorization reports. Based on risks identified for other members of the same RNA-based vaccine platform, the risks listed for BNT162b2 may apply for BNT162b4. Thus, myocarditis and pericarditis are considered a key potential risk for BNT162b4 and are therefore monitored as AESIs, see Section [8.3.8](#).
- Any potential risks that might be associated with the new non-spike antigens encoded by BNT162b4 will be closely monitored throughout the trial.
- As of 20 Dec 2023, no safety concerns have been identified for the combination of BNT162b2 and BNT162b4. Therefore, no new risks or safety concerns are expected for BNT162b4 when administered as monotherapy.

- Potential risks linked to first-in-human (FIH) administration of BNT162b4 will be managed by the planned use of a staggered dosing process with sentinel subjects in Cohorts 1, 2, 3a, and 4a. In addition, the trial IRC will assess whether the tolerability shown up to 7 d post-dose in the sentinel subjects was acceptable and whether any stopping/pausing rules were met. Only when safety and tolerability is confirmed by the IRC will dosing of all other subjects per DL cohort be continued. The IRC will also assess whether the tolerability shown up to 7 d post-dose in all cohort subjects was acceptable and that no stopping/pausing rules were met, before allowing progression to the next higher DL cohort. For Cohort 5, an IRC safety review of available data for Dose 1 and Dose 2 will be performed after all subjects receive Dose 2. For details, including a graphical depiction of the process, see Section 1.1.

For the combination of BNT162b4 and BNT162b2 Bivalent or BNT162b2 Monovalent (OMI XBB.1.5):

- Taking into the account that the total dose of vaccines given in this trial (35, 40, 45, and 60 µg) is higher than the authorized BNT162b2 dose (30 µg), a higher frequency and/or severity of local and systemic reactions cannot be ruled out. However, the trial-specific dose escalation process which includes sentinel subjects at each DL, usage of e-diaries which allows real time control of entered data and defined stopping rules will support appropriate risks minimization measures.

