4 TRIAL DESIGN

4.1 Overall design

This is an exploratory Phase I, randomized, observer-blind, active-controlled, dose-escalation trial to evaluate four DLs of BNT162b4 given in combination with BNT162b2 Bivalent to select a safe and tolerable dose and to evaluate BNT162b4 + BNT162b2 Bivalent when given as Dose 1 and Dose 2 (booster) in Cohorts 1 and 2 and

BNT162b4 + BNT162b2 Monovalent (OMI XBB.1.5) when given as Dose 2 (booster) in Cohorts 3a, 3b, 4a, and 4b, and 30 µg BNT162b4 when given alone as Dose 1 and Dose 2 in Cohort 5.

For flow diagram summaries of the trial, see Section 1.2. For the planned assessments and visits, see the SoAs in Section 1.3 and Section 13.5.

In total, up to ~380 healthy subjects aged 18 yrs and older will be enrolled: up to 60 in each of Cohorts 1, 2, 3a, 3b, 4a, and 4b and ~20 in Cohort 5. For the trial populations (including the planned number of subjects per cohort), dosing regimens, and blinding in Cohorts 1 to 5, see Table 2.

Randomization for enrollment in Cohorts 1, 2, and 3a will be stratified based on N-binding antibody status and CCI

Randomization for enrollment in Cohort 3b will be stratified based on age and N-binding antibody status. Randomization for enrollment in Cohort 4b will be stratified based on age only. All subjects enrolled in Cohorts 4a and 4b, and all subjects giving consent for Dose 2 will be eligible CCI Cohorts 1 to 4 are observer-blind and randomized; Cohort 5 is single arm and open-label.

To minimize heterogeneity between DL cohorts with regard to the baseline N-binding antibody status of subjects, the following subject distribution is planned for each DL cohort when possible: approximately 1/3 N-binding antibody negative subjects and 2/3 N-binding antibody positive subjects in Cohorts 1, 2, 3a, and 3b. However, this distribution can be modified based on the existing prevalence of N-binding antibody negative subjects or operational needs.

Subjects screened to the specific DL cohorts, but not enrolled due to reached N-binding subject distribution rate, will be allowed to be enrolled into the next cohort. Safety laboratory tests (except viral screening) will need to be repeated if performed >28 d prior to the planned IMP vaccination day.

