In addition, depending upon the observed safety and immunogenicity data, the sponsor may update Cohorts 1 to 4 to evaluate higher or additional DLs of BNT162b4 in combination with the selected spike-encoding RNA vaccine BNT162b2 Bivalent or BNT162b2 Monovalent (OMI XBB.1.5).

An IRC will be established and maintained for the entire trial to periodically review subject safety data and make decisions about dose escalations (for details about the IRC, see Section 10.1.5).

The staggered dosing process for Cohorts 1 to 4

The trial will use a staggered dosing process schema with sentinel subjects in Cohorts 1, 2, 3a, and 4a, see Figure 1.

The trial will be initiated with Cohort 1 where eight sentinel subjects will be randomized 3:1 to receive one dose of either BNT162b2 Bivalent + BNT162b4 or control BNT162b2 Bivalent followed by IRC review of 7 d post-Dose 1 data.

If the IRC considers the shown tolerability to be acceptable and no stopping/pausing rules are met, 52 additional trial subjects (expansion group) will be randomized 3:1 to the BNT162b2 Bivalent + BNT162b4 or control group BNT162b2 Bivalent (one dose). Following dosing of the expansion group (7 d post-Dose 1), all available clinical, laboratory

and other relevant data from these 60 trial subjects (full cohort) will be reviewed by the IRC. If the IRC considers the shown tolerability is acceptable and no stopping/pausing rules are met for Cohort 1, enrollment will be opened for Cohort 2. Cohort 2 will follow the same dose escalation/assessment process. For a graphical depiction of the staggered dosing process for Cohorts 1 to 4, see [Figure 1](#).

If the IRC considers the shown tolerability acceptable and no stopping/pausing rules are met for Cohort 2 (for the stopping/pausing rules, see Section [7.1](#)), enrollment will be opened for Cohorts 3a and 3b which will follow the same dose escalation/assessment process as for Cohorts 1 and 2 with the following exception: enrollment for the Cohort 3b will be opened after 7 d post-dose data for Cohort 3a sentinel subjects has been reviewed by the IRC and approval is granted. There will be a safety review of 7 d post-dose data for the first 8 subjects in Cohort 3b. In addition to safety data being reviewed on an ongoing basis by investigators and sponsor, 7 d post-dose data for Cohort 3a expansion subjects and Cohort 3b subjects will be reviewed by the IRC.

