7.1 Discontinuation (stopping) or pausing (temporary halting) of trial treatment

The following pausing rules are established within the trial based on reported AEs, e-diary reactogenicity data, ECG findings, and clinical laboratory results.

Safety data will be reviewed on an ongoing basis by investigators and sponsor.

The sponsor will set up regular IRC meetings (as specified in the IRC Charter). In addition, *ad hoc* IRC meetings will be triggered by reported events that contribute to pausing rules (see Section 7.1.1).

If the sponsor confirms reported events fulfill pausing rules criteria:

- The IRC will review all related data.
- Randomization and trial treatment administration for the impacted cohort(s) will be paused until the IRC recommends that assignment to the cohort and administration of trial treatment may be resumed.

For all trial subjects who are vaccinated, all other routine trial procedures and assessments, including ongoing data entry, reporting of AEs, subject-reporting of reactogenicity in e-diaries, blood draws, and subject follow-up, will continue during the pause.

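### The automatic pause in Section 7.1.1 does not expressly cover the parallel cohort at the same BNT162b4 dose (3a/3b at 15 µg, 4a/4b at 30 µg)

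*Protocol*

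**What the plan says.** Section 7.1.1 of the protocol acts on an event seen in a given cohort and has two limbs. For assignment: "no further trial subjects will be assigned to the cohort". For dosing: "administration of trial treatment in the affected cohort and any higher DLs will be paused until IRC reviews the event(s").

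The parent Section 7.1 adds that, once the sponsor confirms that the criteria are met: "Randomization and trial treatment administration for the impacted cohort(s) will be paused until the IRC recommends that assignment to the cohort" and dosing may resume. It does not say which cohorts count as impacted.

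Section 4.1 lists the age groups as cohorts in their own right: "up to 60 in each of Cohorts 1, 2, 3a, 3b, 4a, and 4b". Table 2 gives 3a and 3b the same BNT162b4 dose (15 µg), and likewise 4a and 4b (30 µg). On timing, "enrollment for the Cohort 3b will be opened after 7 d post-dose data for Cohort 3a sentinel subjects has been reviewed by the IRC"; the committee must also approve. Section 4.1 applies the same review process to 4a and 4b. Table 1 in the Synopsis lists the first-8 reviews in 3b and 4b, and the Dose 2 reviews, as non-gated, which it explains as: "Non-Gated review: trial dosing is not paused while awaiting IRC approval".

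The SAP (Section 1.2, Dose Escalation) refers back to protocol Section 7.1 and adds nothing on scope.

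**The concern.** The automatic pause protects subjects in the interval before anyone has deliberated. The subjects with the most obvious claim to it are those about to receive the dose at which the event occurred. Section 7.1.1 names the cohort of the event and all higher dose levels. It does not name a second cohort at that same dose, although the design creates two such pairs and lets each pair be dosed side by side.

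Read literally, a related serious adverse event in 3a would stop 3a and leave 15 µg dosing in adults over 55 to a further decision. At stake is the period from recognition of the event until the sponsor or the IRC extends the pause. BNT162b4 had not been given to humans before this trial (Section 2.3.2), so that period should be settled by the wording of the rule.

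**Working it through.** **The plan's one related figure.** Table 6 (Section 9.2) gives 0.84 as the chance of at least one event at a true rate of 2% with N = 90. Check: 1 − (1 − 0.02)^90 = 0.838, which agrees. The point does not depend on this figure. It matters only because N = 90 is 45 + 45, so Table 6 pools the two age cohorts at each dose.

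**Step 1: scope of 7.1.1, tested cohort by cohort.**

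| Event in | Other cohort | Is it the affected cohort? | Higher BNT162b4 dose? | Expressly paused? |
|---|---|---|---|---|
| 3a (15 µg) | 3b (15 µg) | No | No | No |
| 3b (15 µg) | 3a (15 µg) | No | No | No |
| 4a (30 µg) | 4b (30 µg) | No | No | No |
| 4b (30 µg) | 4a (30 µg) | No | No | No |
| 4a or 4b (30 µg) | 5 (30 µg alone) | No | No | No |

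This takes *cohort* to mean 3a, 3b, 4a or 4b separately. If it means all subjects at a dose level within Cohorts 1 to 4, the first four rows become Yes.

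**Step 2: can the pairs be dosed at the same time?** One IRC review, of the 3a sentinels, opens both the 3a expansion and Cohort 3b (Table 1); 4a and 4b follow the same pattern. At Dose 1, therefore, they can overlap. Dose 2 falls 6 to 7 months after Dose 1 in all four cohorts (Table 2, footnote d), so an overlap at Dose 1 carries over to Dose 2.

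**Step 3: bounds on the number affected at Dose 1 (BNT162b4 recipients, Table 2).**

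- Cohort 3a: 6 sentinel + 39 expansion = 45. Cohort 3b: 45. Cohorts 4a and 4b have the same numbers.
- Event in 3a or 4a: at most 45 in the sister cohort, reached only if none of them has yet been dosed.
- Event in 3b or 4b: at most 45 − 6 = 39 in the sister cohort, because its sentinels were dosed before 3b or 4b could open.
- Lower bound: 0. This applies if *cohort* is read at dose level, if the sister cohort is already fully dosed, or if it is treated as impacted at once.

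Nothing between 0 and 45 can be derived, because the documents give neither an enrollment rate nor the time until the IRC acts. At Dose 2 only consenting BNT162b4 recipients are dosed, so the ceiling is again 45 per cohort, less those who decline. That number is not given.

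**Step 4: what the other provisions do.**

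- Section 7.1, impacted cohort(s): can include the sister cohort, but is undefined and follows sponsor confirmation.
- Section 8.3.2, reporting within 24 h of events that contribute to a pausing rule: shortens the interval.
- Sections 7.1 and 10.1.5, ad hoc IRC review: leads to a decision and is not itself a stop.
- Sections 4.2 and 7.1.3, power to pause dosing or delay enrollment: discretionary in both places.

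None of these names a cohort at the same dose.

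**The case against.** The best reply is that the rule already reaches the sister cohort. Section 7.1 uses a plural that covers both randomization and dosing. Elsewhere the protocol uses *cohort* at dose level. Section 2.3.2 says: "Only when safety and tolerability is confirmed by the IRC will dosing of all other subjects per DL cohort be continued". Section 4.2 speaks of dose-level cohorts numbered 1 to 4, Section 3 reports by dose-level cohort, and Table 6 pools to 90. On that reading nothing is missing. The IRC Charter, which is not among the documents, may define the term.

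Part of this stands: the dose-level reading is tenable, and the controls in Step 4 make a long gap unlikely. It does not settle the matter. The sentence in 7.1.1 sets *cohort* against *DLs*, which suggests that the two differ. Section 4.1 counts each age group as a cohort, and applies the pausing rules to 3a and 3b by name. Section 2.3.2 shows that the protocol can write *DL cohort* when it means that.

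A reader might also infer more than the documents support:

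- *That an event in 3a halts 30 µg while 15 µg continues.* At Dose 1 this contrast does not arise. Cohorts 4a and 4b open only after the IRC has accepted tolerability in both 3a and 3b (Section 4.1), so no 30 µg dosing is under way.
- *That a definite number of subjects would be exposed per event.* Any figure inside the bounds needs an assumed enrollment rate and IRC response time.
- *That the rule on more than 20% of subjects has the same gap.* It fires only when the IRC makes the determination, so the IRC is already acting. Its wording, "BNT162b4 alone in the same cohort experienced the same or similar", leaves open whether 3a and 3b are counted together, but that is a separate and minor ambiguity.

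**Conclusion.** The gap is real but narrow. As written, the automatic pause does not expressly cover other subjects at the BNT162b4 dose where the event occurred, in two pairs of cohorts that can be dosed concurrently at Dose 1 and again at Dose 2. At Dose 1 the number not expressly covered lies between 0 and 45 BNT162b4 recipients per event (39 at most when the event is in 3b or 4b).

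This rests on reading *cohort* in 7.1.1 as 3a, 3b, 4a or 4b separately. That is the more natural reading of the sentence, but not the only one. The documents do not show that dosing in the sister cohort would in fact continue; the sponsor could well pause both cohorts under Section 7.1. The change is optional but worthwhile, because a safety stop should not depend on which of two tenable readings is applied on the day. Confidence is medium, as the IRC Charter and the current dosing status are not known.

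**What to change.** Reword the opening sentence of 7.1.1 along these lines: *If any of the situations below occurs in a cohort, assignment of subjects and administration of trial treatment are paused in the affected cohort, in any other cohort at the same BNT162b4 DL, and at any higher DLs, until the IRC recommends resumption.* This aligns the assignment and dosing limbs and uses the release condition already in Section 7.1. Align the IRC Charter.

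The cost is one sentence and no new procedure. In operation, an event in one age cohort also holds the other at that dose, usually briefly. A 30 µg event also holds Cohort 5 (20 subjects), and an event in Cohort 5 holds 4a and 4b. Cohort 5 receives 30 µg of RNA in total against 60 µg in Cohort 4, so the sponsor may prefer not to link them. In that case, name the pairs 3a/3b and 4a/4b instead.

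As an optional clarification, state in the >20% rule that 3a, 3b, 4a and 4b are each counted separately. At full enrollment the smallest count above 20% is then 10 of 45 (22.2%), against 19 of 90 (21.1%) if combined. Redefining *cohort* at dose level throughout would close the scope gap, but it would force the combined count.

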If the IRC considers the shown tolerability to be acceptable and no stopping/pausing rules are met, 52 additional trial subjects (expansion group) will be randomized 3:1 to the BNT162b2 Bivalent + BNT162b4 or control group BNT162b2 Bivalent (one dose). Following dosing of the expansion group (7 d post-Dose 1), all available clinical, laboratory and other relevant data from these 60 trial subjects (full cohort) will be reviewed by the IRC. If the IRC considers the shown tolerability is acceptable and no stopping/pausing rules are met for Cohort 1, enrollment will be opened for Cohort 2. Cohort 2 will follow the same dose escalation/assessment process. For a graphical depiction of the staggered dosing process for Cohorts 1 to 4, see [Figure 1](#).

If the IRC considers the shown tolerability acceptable and no stopping/pausing rules are met for Cohort 2 (for the stopping/pausing rules, see Section [7.1](#)), enrollment will be opened for Cohorts 3a and 3b which will follow the same dose escalation/assessment process as for Cohorts 1 and 2 with the following exception: enrollment for the Cohort 3b will be opened after 7 d post-dose data for Cohort 3a sentinel subjects has been reviewed by the IRC and approval is granted. There will be a safety review of 7 d post-dose data for the first 8 subjects in Cohort 3b. In addition to safety data being reviewed on an ongoing basis by investigators and sponsor, 7 d post-dose data for Cohort 3a expansion subjects and Cohort 3b subjects will be reviewed by the IRC.

If the IRC considers the shown tolerability acceptable and no stopping/pausing rules are met for Cohorts 3a and 3b (for the stopping/pausing rules, see Section [7.1](#)), enrollment will be opened for Cohorts 4a and 4b which will follow the same IRC review process as for Cohorts 3a and 3b. In addition to safety data being reviewed on an ongoing basis by investigators and sponsor, 7 d post-dose data for Cohort 4a expansion subjects and Cohort 4b subjects will be reviewed by the IRC.

Dose escalation decisions to progress to the next DL and DL modifications (i.e., dropping the DL to the previous acceptable DL or to an 'in-between' DL) will be confirmed by the IRC. Dose escalation will only continue if the safety and tolerability of the previous DL was considered acceptable by the IRC and no stopping/pausing rules were met.

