10.1.5 Committees – IRC

A trial IRC will be established to provide medical oversight of trial subject safety during the conduct of this trial, with a focus on guidance, management of emergent safety issues, and decision making as outlined in the IRC Charter. It includes periodic in-depth review of safety data by trial subject, cohort, and cumulatively, in order to confirm mechanism of action, identify potential off-target toxicities, and to understand the IMP's safety profile and feasibility for further clinical development. The IRC is also a forum for the discussion of other data which could impact the IMP benefit-risk assessment, thereby allowing the IRC to periodically assess the overall benefit-risk of the IMP.

All SAEs considered related either by the investigator or the sponsor will trigger an *ad hoc* review by the IRC.

The IRC will be constituted and act according to procedures described in the IRC Charter. The charter will define suitable measures to maintain the blinding described in Section 6.3.2. The IRC will prepare written minutes of its meetings. Documentation of IRC activities will be filed in the trial master file.

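### The SAE pausing rule in Protocol Section 7.1.1 requires both relatedness and no alternative cause, so a related SAE below Grade 4 with a plausible alternative cause generally starts no automatic pause

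*Protocol*

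**What the plan says.** Section 7.1.1 of the protocol lists six situations. Any one of them stops assignment to the cohort, and stops dosing in that cohort and any higher dose level, until the IRC has reviewed the event. Data from recipients of BNT162b2 Bivalent alone do not count.

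- **SAE:** an SAE in a BNT162b4 recipient "for which there is no alternative, plausible, attributable cause and which is assessed by the investigator, or the sponsor as possibly related".
- **Grade 4 AE, and persistent fever above 40.0°C:** an event "that is assessed as possibly related by the investigator, or for which there is no alternative, plausible, attributable cause".
- **More than 20% of recipients in a cohort with the same or a similar unsolicited AE of Grade 3 or above:** "considered related, and/or for which there is no alternative, plausible, attributable cause".
- **Severe hypersensitivity or anaphylaxis:** an event "that occurs within 7 d of trial treatment administration for which there is no alternative, plausible, attributable cause".
- **Myocarditis or pericarditis:** "Any case of myocarditis or pericarditis documented within 28 d after" a BNT162b4-containing dose, with supporting ECG or laboratory findings and no causality condition.

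Under Section 7.1, once the sponsor confirms that a criterion is fulfilled, randomization and dosing in the affected cohort "will be paused until the IRC recommends that assignment to the cohort and administration of trial treatment may be resumed". Section 10.1.5 separately provides: "All SAEs considered related either by the investigator or the sponsor will trigger an" ad hoc IRC review. It does not say that dosing stops meanwhile. Section 4.2 lets the IRC pause or stop at any time. Under the Synopsis (Section 1.1), dose escalation continues only if the safety and tolerability of the previous level "was considered acceptable by the IRC and no stopping/pausing rules were met".

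**The concern.** An SAE can be related and still have a plausible alternative cause. Section 10.4.3 defines related as a reasonable possibility of causation, judged after alternative causes have been considered. If being related and having no alternative cause meant the same thing, the choice offered in the Grade 4 and fever bullets would be empty. The SAE bullet therefore applies the alternative-cause test a second time, as a separate hurdle.

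The result is out of order. A non-serious Grade 4 AE that the investigator judges related pauses the cohort even when another cause is plausible. A related Grade 3 event requiring hospitalization, with the same alternative cause, does not meet the SAE bullet. Mixed attributions are foreseeable, because stable pre-existing disease is allowed (Section 5.1.1) and about 60% of Cohorts 3b and 4b are to be aged 65 or over (Table 2).

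Two things are at stake in this first-in-human trial. Assignment and dosing may continue between the SAE report and the ad hoc review. The event also does not count as a pausing rule met when escalation is decided, which leaves the IRC's own tolerability judgment as the remaining check.

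**Working it through.** The plan states no figure to reproduce. The check reads each bullet as a logical condition. Let I = investigator judges related, S = sponsor judges related, N = no plausible alternative cause.

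| Bullet in 7.1.1 | Causality condition | Related SAE below Grade 4, N false |
|---|---|---|
| SAE | N and (I or S) | Not met |
| Grade 4 AE | I or N | Not met: grade too low |
| Fever above 40.0°C | I or N | Not met: such a fever is Grade 4 (Table 5) |
| More than 20% cluster | related and/or N | Met only if the cluster exists |
| Hypersensitivity | N | Not met |
| Myocarditis/pericarditis | none | Met only if the event is such a case |

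**Count.** Both conditions required: 1. Either accepted: 3. N alone required: 1. No causality condition: 1. Total: 1 + 3 + 1 + 1 = 6.

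**What the SAE bullet adds.** Any Grade 4 SAE that meets it has N true, and so already meets the Grade 4 bullet. The SAE bullet can extend coverage only below Grade 4, and there it excludes every SAE with a plausible alternative cause.

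**Can such SAEs occur?** Yes. Section 10.4.2.1 requires severity and seriousness to be assessed independently. Section 10.4.2 includes hospitalization, and important medical events that are not immediately life-threatening. The general Grade 4 definition in Section 10.4.3 requires life-threatening consequences.

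**Solicited reactions.** Tables 4 and 5 have 3 + 8 = 11 rows. Emergency room attendance or hospitalization for the symptom is already Grade 4 in seven: pain, diarrhea, headache, fatigue, myalgia, arthralgia and chills. Vomiting is not an eighth: its Grade 4 entry needs hypotensive shock, and intravenous hydration is Grade 3. Erythema, induration and fever are graded on other criteria. The gap therefore mainly concerns unsolicited SAEs.

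**The cluster bullet as a backstop.** Assume the denominator is the BNT162b4 recipients dosed so far in the cohort, which the protocol does not specify. The smallest number of similar events exceeding 20% of n is floor(0.2n) + 1:

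- n = 4: 1 (1/4 = 25%)
- n = 5: 2 (1/5 = 20% does not exceed 20%)
- n = 6 (sentinel recipients): 2
- n = 20 (Cohort 5): 5
- n = 45 (full recipient group): 10 (9/45 = 20% does not exceed 20%)

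A single event meets this bullet only while at most four recipients have been dosed, and only if it is unsolicited and Grade 3 or above.

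**Where reviews do not hold dosing.** In Table 1 the gated reviews follow the sentinel groups and precede each dose-level increase, all after Dose 1. Every Dose 2 review is non-gated. Cohort 5 has a single non-gated review, after all subjects have received Dose 2.

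**Effect of deleting N.** The bullet becomes I or S. The only cases added are those with (I or S) true and N false. All of them already require ad hoc review under Section 10.1.5.

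**The case against.** The strongest reply is that the affected set is small and well guarded. Investigators already weigh alternative causes, so many SAEs with a convincing alternative will be judged not related. The event must also be below Grade 4, not myocarditis or pericarditis, and not part of a cluster. SAEs reach the sponsor within 24 h (Sections 8.3.2 and 10.4.4), investigators raise safety concerns immediately (Section 7), and safety data are reviewed continuously (Section 7.1). The IRC may pause at any time, and the sponsor may suspend the whole trial for any reason (Section 10.7.1). Gated reviews prevent dosing from passing a sentinel gate or opening the next dose level without IRC approval. The IRC Charter, which is not among these documents, may set a deadline for ad hoc review or an interim hold.

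Most of this stands, and it limits the practical gap. None of it restores the automatic pause. The gates do not act within an expansion already open, at a higher dose level already being dosed, at Dose 2, or in Cohort 5.

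A reader might infer that these SAEs escape oversight, or that dosing would in fact continue for long. The documents do not support either. Section 10.1.5 makes the review mandatory, and the absence of a stated review time is not evidence of delay. Nor do all related SAEs with an alternative cause escape the pause: a Grade 4 event that the investigator judges related meets the Grade 4 bullet.

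**Conclusion.** The point holds as a narrow but real inconsistency in a safety rule, and it should be fixed. Unless the myocarditis/pericarditis bullet or the cluster bullet applies, a related SAE below Grade 4 with a plausible alternative cause leads to mandatory ad hoc review and a possible discretionary pause, but no automatic one. The protocol gives no reason for a narrower trigger for SAEs than for Grade 4 AEs.

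The conclusion rests on the plain wording of Section 7.1.1 and on the definition of related in Section 10.4.3. The cluster thresholds rest on the denominator assumed above. Neither the number of affected events nor the number of subjects dosed in the interval can be estimated, because the documents give no SAE rate and no time to ad hoc review.

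**What to change.** Delete the alternative-cause clause from the SAE bullet in Section 7.1.1. It would then cover any SAE in a subject given BNT162b4, alone or in combination, that either the investigator or the sponsor judges possibly related. This matches the review trigger in Section 10.1.5, which needs no change. It would also catch a Grade 4 SAE that only the sponsor judges related and that has a plausible alternative cause; the Grade 4 bullet misses that event because it counts only the investigator's assessment.

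The cost is one wording edit and an occasional temporary pause until a review that is already required.

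A second trigger for SAEs with no plausible alternative cause, as in the Grade 4 bullet, is optional and not needed to close the gap. It would pause dosing for SAEs that both parties judge unrelated, for which Section 10.1.5 requires no review. The SAE bullet has no time limit, and SAEs are recorded for about 6 months after each dose in Cohorts 1 to 4, so an unexplained late event could trigger it.
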